AST	Aspartate Aminotransferase
BP	blood pressure
BUN	Blood Urea Nitrogen
CAD	Coronary artery disease
CD	carbohydrate-deficient
CD-ROM	Compact Disc – Read Only Memory
CHF	chronic heart failure
CK	Creatine Kinase
CKD	Chronic kidney disease
CMO&PS	Chief Medical Office and Patient Safety
CMV	Cytomegalovirus
COVID-19	Coronavirus disease 2019
CRF	Case Report/Record Form (paper or electronic)
CRO	Contract Research Organization
CV	Cardiovascular
CVD	Cardiovascular disease
DDE	Direct Data Entry
DILI	Drug-induced liver injury
DMC	Data monitoring committee
EAS	European Atherosclerosis Society
EBV	Epstein-Barr virus
ECG	Electrocardiogram
eCRF	Electronic Case Report Form
EDC	Electronic Data Capture
eGFR	Estimated glomerular filtration rate
EMA	Europeans Medicines Agency
ERCP	Endoscopic retrograde cholangiopancreatography
eSAE	Electronic Serious Adverse Event
ESC	European Society of Cardiology
FH	Familial hypercholesterolemia

GalNAc	N-Acetylgalactosamine
GCP	Good Clinical Practice
GCS	Global Clinical Supply
G-CSF	Granulocyte-colony stimulating factor
GGT	Gamma-glutamyl transferase
GLDH	glutamate dehydrogenase
h	Hour
HAV	Hepatitis A Virus
HbA1c	Hemoglobin A1c
HBc	Hepatitis B core
HBsAg	Hepatitis B surface antigen
HBV	Hepatitis B Virus
hCG	Human chorionic gonadotropin
HCV	Hepatitis C Virus
HDL-C	high-density lipoprotein cholesterol
HeFH	heterozygous familial hypercholesterolemia
HEV	Hepatitis E Virus
HIV	Human immunodeficiency virus
HoFH	Homozygous familial hypercholesterolemia
hsCRP	high sensitivity C-reactive protein
HSV	Herpes Simplex Virus
IA	Interim analysis
IAS	International Atherosclerosis Society
IB	Investigator's Brochure
ICF	Informed Consent Form
ICH	International Council for Harmonization of Technical Requirements for Pharmaceuticals for Human Use
IEC	Independent Ethics Committee
IFN	Interferon
IgA	Immunoglobulin A
IgE	Immunoglobulin E
IgG	Immunoglobulin G
IgM	Immunoglobulin M
IL	Interleukin
IN	Investigator Notification
INR	International Normalized Ratio
IP-10	Interferon-gamma-inducible protein 10
IRB	Institutional Review Board
IRT	Interactive Response Technology
ISR	injection site reaction
IUD	intrauterine device
IUS	intrauterine system
JAS	Japan Atherosclerosis Society
LDH	Lactate dehydrogenase
LDL	Low-density lipoprotein
LDL-C	Low-density lipoprotein cholesterol
LDLR	Low-density lipoprotein receptor

LFT	Liver function test
LLN	lower limit of normal
LMT	lipid-modifying therapies
Lp(a)	lipoprotein a
MAR	missing at random
MCH	Mean cell hemoglobin
MCHC	Mean corpuscular hemoglobin concentration
MCV	mean corpuscular volume
MedDRA	Medical dictionary for regulatory activities
mg	milligram(s)
MI	myocardial infarction
mL	milliliter(s)
MMRM	Mixed Model with Repeated Measurement
MRI	Magnetic resonance imaging
mRNA	Messenger ribonucleic acid
NLA	National Lipid Association
NYHA	New York Heart Association
PAD	Peripheral artery disease
PCR	Protein-creatinine ratio
PCS	potentially clinically significant
PCSK9	Proprotein convertase subtilisin/kexin type 9
PD	Pharmacodynamic(s)
████████	
PT	prothrombin time
QMS	Quality Management System
QTcF	QT interval corrected by Fridericia's formula
R Value	ALT/ALP x ULN
RBC	red blood cell(s)
RISC	RNA-induced silencing complex
RNA	Ribonucleic acid
s.c.	subcutaneous
SAE	Serious Adverse Event
SAP	Statistical Analysis Plan
siRNA	small interfering ribonucleic acid
SMQ	Standardized MedDRA Query
SoC	Standard of Care
SOP	Standard Operation Procedure
SUSAR	Suspected Unexpected Serious Adverse Reaction
████████	
TBL	total bilirubin
TEAE	treatment-emergent adverse event
████████	
TNF- α	Tumor necrosis factor-alpha
TSH	thyroid stimulating hormone
ULN	upper limit of normal
UTI	Urinary Tract Infection
VLDL-C	very low-density lipoprotein cholesterol

[REDACTED]

WBC white blood cell(s)

WHO World Health Organization

WoC Withdrawal of Consent

Glossary of terms

Additional treatment	Medicinal products that may be used during the clinical trial as described in the protocol, but not as an investigational medicinal product (e.g. any background therapy)
Assessment	A procedure used to generate data required by the study
Dosage	Dose of the study treatment given to the participant in a time unit (e.g. 100 mg once a day, 75 mg twice a day)
Electronic Data Capture (EDC)	Electronic data capture (EDC) is the electronic acquisition of clinical study data using data collection systems, such as Web-based applications, interactive voice response systems and clinical laboratory interfaces. EDC includes the use of Electronic Case Report Forms (eCRFs) which are used to capture data transcribed from paper source forms used at the point of care
Enrollment	Point/time of participant entry into the study at which informed consent must be obtained
Estimand	A precise description of the treatment effect reflecting the clinical question posed by the trial objective. It summarizes at a population-level what the outcomes would be in the same patients under different treatment conditions being compared. Attributes of an estimand include the population, variable (or endpoint) and treatment of interest, as well as the specification of how the remaining intercurrent events are addressed and a population-level summary for the variable.
Inclisiran	In this protocol, the dose is shown with inclisiran sodium unless otherwise specified. Inclisiran is also referred to as KJX839. 300 mg inclisiran sodium is equivalent to 284 mg inclisiran. 200 mg inclisiran sodium is equivalent to 189 mg inclisiran. 100 mg inclisiran sodium is equivalent to 94.5 mg inclisiran.
Intercurrent events	Events occurring after treatment initiation that affect either the interpretation or the existence of the measurements associated with the clinical question of interest.
Investigational drug/ treatment	The drug whose properties are being tested in the study
Medication number	A unique identifier on the label of medication kits
Mis-randomized participants	Mis-randomized participants are those who were not qualified for randomization and who did not take study treatment, but have been inadvertently randomized into the study
Other treatment	Treatment that may be needed/allowed during the conduct of the study (i.e. concomitant or rescue therapy)
Part	A sub-division of a study used to evaluate specific objectives or contain different populations. For example, one study could contain a single dose part and a multiple dose part, or a part in participants with established disease and in those with newly-diagnosed disease
Participant	A trial participant (can be a healthy volunteer or a patient)
Participant number	A unique number assigned to each participant upon signing the informed consent. This number is the definitive, unique identifier for the participant and should be used to identify the participant throughout the study for all data collected, sample labels, etc.
Period	The subdivisions of the trial design (e.g. Screening, Treatment, Follow-up) which are described in the Protocol. Periods define the study phases and will be used in clinical trial database setup and eventually in analysis
Personal data	Participant information collected by the Investigator that is coded and transferred to Novartis for the purpose of the clinical trial. This data includes participant identifier information, study information and biological samples.
Randomization number	A unique identifier assigned to each randomized participant
Screen Failure	A participant who did not meet one or more criteria that were required for participation in the study
Source Data/Document	Source data refers to the initial record, document, or primary location from where data comes. The data source can be a database, a dataset, a spreadsheet or even hard-coded data, such as paper or eSource

Start of the clinical trial	The start of the clinical trial is defined as the signature of the informed consent by the first participant
Study treatment	Any drug or combination of drugs or intervention administered to the study participants as part of the required study procedures; includes investigational drug(s), control(s) or background therapy
Study treatment discontinuation	When the participant permanently stops taking any of the study drug(s) prior to the defined study treatment completion date (if any) for any reason; may or may not also be the point/time of study discontinuation
Treatment arm/group	A treatment arm/group defines the dose and regimen or the combination, and may consist of 1 or more cohorts.
Treatment of interest	The treatment of interest and, as appropriate, the alternative treatment to which comparison will be made. These might be individual interventions, combinations of interventions administered concurrently, e.g. as add-on to standard of care, or might consist of an overall regimen involving a complex sequence of interventions. This is the treatment of interest used in describing the related clinical question of interest, which might or might not be the same as the study treatment.
Variable (or endpoint)	The variable (or endpoint) to be obtained for each participant that is required to address the clinical question. The specification of the variable might include whether the participant experiences an intercurrent event.
Withdrawal of study consent (WoC)	Withdrawal of consent from the study occurs only when a participant does not want to participate in the study any longer and does not allow any further collection of personal data

Amendment 1

Amendment rationale

The main purpose of this amendment is based on the Health Authority request below:

- The exclusion criteria #9 (uncontrolled hypertension: systolic blood pressure >180 mmHg or diastolic blood pressure >110 mmHg) was revised. Health Authority commented that participants with systolic blood pressure >160 mmHg or diastolic blood pressure >100 mmHg, who require immediate treatment of hypertension, cannot be enrolled in this study from the safety standpoint. Therefore, the exclusion criteria was revised to exclude the participants with systolic blood pressure >160 mmHg or diastolic blood pressure >100 mmHg.

[REDACTED]

- Several safety assessments were added.

[REDACTED]

The amendment further corrected two small inconsistencies, between the protocol and the pregnancy follow-up informed consent form regarding the length of the follow-up period in case of a pregnancy, and the [Table 6-3](#) for blinding levels.

Furthermore, some minor changes and corrections of inconsistencies and typographical errors have been done.

Changes to the protocol

The revisions made to the protocol are listed below.

- [Section 3, Section 4.1](#): [REDACTED]
- [Section 5.2](#): Exclusion criteria #9 was revised. [REDACTED]
- [Section 6.4](#): The blinding level in case of Safety event (single participant unblinded) in [Table 6-3](#) was corrected to align with the emergency breaking case in [Section 6.6.3](#).
- [Table 8-1](#): Safety assessments were added.
- [Section 8.4](#): Safety assessments were added in [Table 8-2](#) and [Table 8-3](#).
- [Section 8.4.5](#): Appropriateness of safety measurement was added.

- **Section 10.1.4:** To align with the pregnancy follow-up informed consent form, a small adjustment was made to the length of the follow-up period in case of a pregnancy: “until one year after birth” is replaced by “until one year after the baby was due to be born”.
- **Section 12.5.2:** Minor changes were made in the output method.

Other minor corrections/clarifications were made where applicable. Changes to specific sections of the protocol are shown in the track changes version of the protocol using strike through red font for deletions and red underlined for insertions.

IRBs/IECs

A copy of this amended protocol will be sent to the IRBs/IECs and Health Authorities.

The changes described in this amended protocol require IRB/IEC and Health Authority approval according to local regulations prior to implementation.

Protocol summary

Protocol number	CKJX839A11201
Full Title	A placebo-controlled, double-blind, randomized trial to evaluate the effect of different doses of inclisiran given as subcutaneous injections in Japanese participants with high cardiovascular risk and elevated low-density lipoprotein cholesterol (LDL-C) (ORION-15)
Brief title	Study of efficacy and safety of inclisiran in Japanese participants with high cardiovascular risk and elevated LDL-C
Sponsor and Clinical Phase	Novartis Phase II
Investigation type	Drug
Study type	Interventional
Purpose and rationale	The aim of the ORION-15 protocol is to evaluate the pharmacodynamic response in Japanese participants [REDACTED] [REDACTED] [REDACTED]
Primary Objective(s)	The primary objective of this study is to demonstrate superiority of inclisiran treatment at different dose levels (100 mg, 200 mg, and 300 mg) to placebo on LDL-C levels at Day 180.
Secondary Objectives	The secondary objectives of this study are: To evaluate the effect of inclisiran until Day 180 on the following: 
• PCSK9 levels over time• LDL-C levels over time• Other lipids, lipoproteins, apolipoproteins (total cholesterol, triglycerides, HDL-C, non-HDL-C, VLDL-C, Apo-A1, Apo-B, and Lp(a))• Proportion of participants achieving lipid control target pre-specified by JAS 2017 guideline• Individual responsiveness to different doses To evaluate safety and tolerability profile of inclisiran
Study design	This is a placebo-controlled, double-blind, randomized trial in Japanese participants. 308 eligible participants will be randomized to inclisiran sodium 300 mg (n=100), inclisiran sodium 200 mg (n=100), inclisiran sodium 100 mg (n=54), and placebo (n=54). The expected duration of the participants' involvement in the study will be approximately 374 days which includes screening (up to 14 days), Day 1 study drug administration, two additional injections on Day 90 and Day 270, and the follow-up period to Day 360. [REDACTED]
Study population	This trial includes Japanese participants with history of coronary artery disease (CAD) or participants categorized in 'high risk' by JAS 2017 guideline (diabetes, chronic kidney disease (CKD), non-cardiogenic cerebral infarction, peripheral artery disease (PAD) or combination of other risk factors and categorized in 'high risk' assessed by Saita Score), or participants with heterozygous familial hypercholesterolemia (HeFH) and elevated LDL-C.

Key Inclusion criteria	
Male or female participants ≥ 20 years of age.Participants with history of CAD or participants categorized in 'high risk' by JAS 2017 guideline (diabetes, CKD, non-cardiogenic cerebral infarction, PAD or combination of other risk factors and categorized in 'high risk' assessed by Suita Score), or participants with HeFH diagnosed by JAS 2017 guideline.As per the JAS 2017 guideline, participants should meet serum LDL-C value at screening as follow:
Serum LDL-C ≥ 70 mg/dL for participants with history of CAD with additional risk factors such as HeFH, acute coronary syndrome (ACS) or diabetes complicated by other risk factors (non-cardiogenic cerebral infarction, PAD, CKD, metabolic syndrome, overlap of major risk factors, smoking)Serum LDL-C ≥ 100 mg/dL for participants with history of CAD without additional risk factors or HeFH participants without CAD historySerum LDL-C ≥ 120 mg/dL for participants categorized in 'high risk'Fasting triglyceride <4.52 mmol/L (<400 mg/dL) at screening.Estimated glomerular filtration rate (eGFR) calculated with the revised equations for eGFR in Japan (Matsuo et al 2009) >30 ml/min/1.73 m² at screening.Participants on statins should be receiving a maximally tolerated dose. Maximum tolerated dose is defined as the maximum dose of statin that can be taken on a regular basis without intolerable adverse events (AE). Intolerance to any dose of any statin must be documented as historical AEs attributed to the statin in question in the source documentation and an appropriate electronic Case Report Form (eCRF).Participants not receiving statins must have documented evidence of intolerance to at least one statin.For all participants, the lipid-lowering therapy should have remained stable (stable dose and no medication change) for ≥ 30 days before screening with no planned medication/ dose change until Day 180
Key Exclusion criteria	
Participants diagnosed with homozygous familial hypercholesterolemia (HoFH).Any uncontrolled or serious disease, or any medical or surgical condition, that may either interfere with participation in the clinical study, and/or put the participant at significant risk (according to investigator's judgment) if he/she participates in the clinical study.New York Heart Association (NYHA) class IV heart failure or last known left ventricular ejection fraction $<25\%$.Cardiac arrhythmia within 3 months prior to randomization that is not controlled by medication or via ablation.Major adverse cardiovascular event within 3 months prior to randomization.Uncontrolled hypertension: systolic blood pressure >160 mmHg or diastolic blood pressure >100 mmHg prior to randomization despite antihypertensive therapy.Active liver disease defined as any known current infectious, neoplastic, or metabolic pathology of the liver or unexplained elevations in alanine aminotransferase (ALT), aspartate aminotransferase (AST), $>3x$ the upper limit of normal (ULN), or total bilirubin $>2x$ ULN at screening confirmed by a repeat abnormal measurement at least 1 week apart.Severe concomitant non-cardiovascular disease that carries the risk of reducing life expectancy to less than 2 years.Treatment (within 90 days of screening) with monoclonal antibodies directed towards PCSK9.
Study treatment	Study treatment will be administered as a single s.c. injection of one of below arms on Day 1, Day 90 and Day 270. 
300 mg inclisiran sodium (equivalent to 284 mg inclisiran)200 mg inclisiran sodium (equivalent to 189 mg inclisiran)100 mg inclisiran sodium (equivalent to 94.5 mg inclisiran)Placebo Inclisiran is also referred to as KJX839.
Treatment of interest	The randomized treatment (inclisiran or placebo) with individualized, optimal standard of Care (SoC) lipid-lowering treatment. The dose of the permitted lipid-lowering medications must have remained stable for ≥ 30 days before screening with no

	planned medication or dose change until Day 180. Further details are provided in Section 6 .
Efficacy assessments	LDL-C, total cholesterol, triglycerides, HDL-C, non-HDL-C, very low-density lipoprotein cholesterol (VLDL-C), apolipoprotein A1 (Apo-A1), apolipoprotein B (Apo-B), lipoprotein(a) [Lp(a)], and PCSK9
Pharmacodynamic assessments	Mentioned in efficacy assessments
Key safety assessments	AEs, SAEs, vital signs, clinical laboratory values (hematology, coagulation, biochemistry, steroid hormones, and urinalysis), and electrocardiograms (ECGs), ADA
Other assessments	
Data analysis	The primary analysis on percentage of change in LDL-C from baseline to Day 180 will be performed using a MMRM (Mixed Model with Repeated Measurement) model at a one-sided significance alpha level of 0.025. Same analysis will also be performed on key secondary endpoints, and summary statistics will be provided for all efficacy and safety analysis.
Key words	inclisiran, PCSK9, Hypercholesterolemia, LDL-C

1 Introduction

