4.5 Risks and benefits

Reduction of LDL-C has been associated with reduced cardiovascular risk both by epidemiology and in controlled clinical trials. Injection site reaction is the only event known to be attributed to inclisiran treatment. The safety profile of inclisiran observed to date is considered acceptable for this clinical trial.

[figure not shown]
The risk to participants in this trial may be minimized by compliance with the eligibility criteria and study procedures, as well as close clinical monitoring, close clinical monitoring of safety parameters, as well as periodic review of the safety data by an independent data monitoring committee (DMC). Participants will also be observed in the clinic for at least 4 hours post injection on Day 1 (first dosing of inclisiran) and for at least 30 minutes post injection on Day 90 and Day 270 before being discharged.

Women of child-bearing potential must be informed that taking the study treatment may involve unknown risks to the fetus if pregnancy was to occur during the study, and agree that in order to participate in the study they must adhere to the contraception requirements outlined in the exclusion criteria. If there is any question that the participant will not reliably comply, they should not be entered or continue in the study.

5 Study Population

This will be a multi-center study conducted in Japan. A total of approximately 308 randomized Japanese participants are planned for inclusion in the study: 100 participants per each of two inclisiran sodium dose groups (200 mg and 300 mg); plus 54 participants in the 100mg inclisiran sodium dose and the placebo groups. Since 23% screening failure rate is expected, approximately 400 participants will be screened.

It is intended to enroll approximately 30 participants with HeFH in total.

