5.2 Exclusion criteria

Participants meeting any of the following criteria are not eligible for inclusion in this study.

1. Use of other investigational drugs within 5 half-lives of enrollment within 30 days (e.g. small molecules) / or until the expected pharmacodynamic effect has returned to baseline (e.g. biologics), whichever is longer; or longer if required by local regulations.
2. History of hypersensitivity to any of the study treatments or its excipients or to drugs of similar chemical classes.
3. Participants diagnosed with homozygous familial hypercholesterolemia (HoFH).
4. Any uncontrolled or serious disease, or any medical or surgical condition, that may either interfere with participation in the clinical study, and/or put the participant at significant risk (according to investigator's judgment) if he/she participates in the clinical study.
5. An underlying known disease, or surgical, physical, or medical condition that, in the opinion of the investigator (or delegate) might interfere with interpretation of the clinical study results.
6. New York Heart Association (NYHA) class IV heart failure or last known left ventricular ejection fraction $<25\%$.
7. Cardiac arrhythmia within 3 months prior to randomization that is not controlled by medication or via ablation.
8. Major adverse cardiovascular event within 3 months prior to randomization.
9. Uncontrolled hypertension: systolic blood pressure >160 mmHg or diastolic blood pressure >100 mmHg prior to randomization despite antihypertensive therapy.
10. Active liver disease defined as any known current infectious, neoplastic, or metabolic pathology of the liver or unexplained elevations in alanine aminotransferase (ALT),

aspartate aminotransferase (AST), >3x the upper limit of normal (ULN), or total bilirubin >2x ULN at screening confirmed by a repeat abnormal measurement at least 1 week apart. The repeat test should be done and confirmed before the randomization.

11. Severe concomitant non-cardiovascular disease that carries the risk of reducing life expectancy to less than 2 years.
12. History of malignancy of any organ system (other than localized basal cell carcinoma of the skin or in situ cervical cancer), treated or untreated, within the past 5 years, or if diagnosed between screening visit and randomization visit regardless of whether there is evidence of local recurrence or metastases

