- If local regulations deviate from the contraception methods listed above to prevent pregnancy, local regulations apply and will be described in the ICF.

15. Known history of alcohol and/or drug abuse within the last 5 years.

16. Planned use of other investigational products or devices during the course of the study.
17. Any condition that according to the investigator could interfere with the conduct of the study, such as but not limited to:
 - Participants who are unable to communicate or to cooperate with the investigator.
 - Unable to understand the protocol requirements, instructions and study-related restrictions, the nature, scope, and possible consequences of the study (including participants whose cooperation is doubtful due to drug abuse or alcohol dependency).
 - Unlikely to comply with the protocol requirements, instructions, and study-related restrictions (e.g., uncooperative attitude, inability to return for follow-up visits, and improbability of completing the study).
 - Have any medical or surgical condition, which in the opinion of the investigator would put the participant at increased risk from participating in the study.
 - Persons directly involved in the conduct of the study.
18. Treatment (within 90 days of screening) with monoclonal antibodies directed towards PCSK9.
19. Participants who need LDL-C apheresis treatment.

6 Treatment

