6.2.1.1 Permitted concomitant therapy requiring caution and/or action

The following medications/treatments are permitted during the study:

- Hormone replacement therapy

- Lipid-lowering medications; participants on lipid-lowering medications (such as statins and/or ezetimibe) should be on a stable dose for ≥ 30 days before screening with no planned medication or dose change until Day 180
- Prescription medications prescribed to treat pre-existing medical conditions such as diabetes and hypertension
- Prescription or non-prescription medications, when necessary to treat an AE, and at the discretion of the investigator

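### Exclusion 9 applies its 160/100 mmHg limit only to people already on antihypertensive therapy, so no numeric limit covers untreated participants

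*Protocol*

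**What the plan says.** Criterion 9 appears in the Protocol summary (Key Exclusion criteria) and in Section 5.2 with the same wording: "Uncontrolled hypertension: systolic blood pressure >160 mmHg or diastolic blood pressure >100 mmHg prior to randomization despite antihypertensive therapy".

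Three other exclusions in Section 5.2 could be applied to a person with high blood pressure. None gives a number.

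- Exclusion 4 covers uncontrolled or serious disease and other conditions that may interfere with participation or "put the participant at significant risk (according to investigator's judgment) if he/she participates in the clinical study".
- Exclusion 5 covers a condition that "in the opinion of the investigator (or delegate) might interfere with interpretation of the clinical study results".
- Exclusion 17 includes a medical or surgical condition "which in the opinion of the investigator would put the participant at increased risk from participating in the study".

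The Amendment 1 rationale gives the reason for the current limit. The Health Authority's comment was that people above 160 or 100 mmHg, "who require immediate treatment of hypertension, cannot be enrolled in this study from the safety standpoint". The sponsor's stated response was that "the exclusion criteria was revised to exclude the participants with systolic blood pressure >160 mmHg or diastolic blood pressure >100 mmHg". Neither sentence sets a condition on existing therapy.

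**The concern.** Pressure can be high in spite of a treatment only if the treatment is being taken. As worded, the criterion therefore reaches treated people whose pressure remains above the limit, and it misses people above the limit who take nothing. Yet a person found at screening with untreated pressure above 160/100 mmHg is the plainest example of someone who may need treatment started at once, which is the stated reason for the limit.

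What is at stake is consistency of a safety rule. The sponsor chose a fixed number. For untreated people that number gives way to individual judgement at approximately 50 sites (Section 3), which may not all decide alike. The situation is foreseeable in this population. One entry route is the Suita score, where pressure of 160 systolic or 100 diastolic and above adds 6 points using the current reading, whether or not the patient is treated (Figure 16-2). High untreated pressure can thus move a person towards inclusion while falling outside the numeric exclusion.

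**Working it through.** The plan states no figure to reproduce, so the check is a reading of the text.

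**Step 1: find every blood pressure number that could decide eligibility.**

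| Place | Blood pressure number | Does it exclude anyone? |
|---|---|---|
| Section 5.1, inclusion criteria 1 to 9 | None in the criteria themselves | No |
| Section 5.2, exclusion 9 | 160/100 mmHg | Yes, subject to the therapy condition |
| Section 5.2, the other 18 exclusions | None | Not by a number |
| Figure 16-2, Suita score | Bands up to 160/100 mmHg and above | No; it adds risk points |
| Protocol Table 16-1 and SAP Table 2.8 | Notable values, e.g. systolic above 200 mmHg | No; they flag abnormal values and do not set eligibility |

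Of the 19 exclusions, 1 contains a blood pressure number and 0 contain one that applies to an untreated person.

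**Step 2: apply exclusion 9 literally to example readings.**

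| Reading before randomization | On antihypertensive therapy | Not on antihypertensive therapy |
|---|---|---|
| 165/95 mmHg | Excluded by no. 9 | Not reached by no. 9 |
| 185/115 mmHg | Excluded by no. 9 | Not reached by no. 9 |

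A treated person at 165/95 is excluded by rule. An untreated person at 185/115 is not.

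**Step 3: see what remains for the untreated person.** Exclusions 4, 5 and 17 (3 of 19) are available, all resting on the investigator's judgement or opinion. Exclusion 5 concerns interpretation of results, so the realistic safety backstops are 4 and 17.

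**Step 4: compare with the wording of a neighbouring criterion.** Exclusion 7 concerns arrhythmia not controlled by medication or ablation. That form of words can include a person who has had neither. Exclusion 9 is built differently and presupposes treatment.

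**Step 5: test the change.** With the therapy condition removed, all four cells in Step 2 read as excluded by no. 9.

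**The case against.** The best case for the current text has four parts.

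1. *The definition is coherent.* A sponsor may define uncontrolled hypertension as pressure above a limit in spite of therapy. The amendment rationale summarises thresholds; it describes the previous limit by its numbers alone as well, so its silence on therapy is weak evidence that the condition was meant to go. The amended protocol also needed Health Authority approval before implementation. This limits what can be inferred: the documents do not show the authority's view of the therapy condition. It does not remove the gap, which lies in the operative criterion, and the reference to immediate treatment still describes untreated people more naturally than treated ones.

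2. *The gap is narrow in practice.* An investigator can read the words before the colon broadly, or use exclusion 4. If treatment is started during the screening period of up to 14 days, the person is then on therapy and criterion 9 applies. Later safeguards also exist: vital signs before each injection (Table 8-1), interruption of dosing judged detrimental (Section 6.5.1), and discontinuation for safety risk (Section 9.1.1). These reduce the consequence, and that stands. But whether to act is a matter of judgement in each case, so none of them restores the fixed limit.

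3. *The risk is small.* Section 6.2.1.1 permits "Prescription medications prescribed to treat pre-existing medical conditions such as diabetes and hypertension" during the study, and Section 4.5 states that "Injection site reaction is the only event known to be attributed to inclisiran treatment". This stands, and it is why the point is minor. The counts of criteria above describe the wording; they do not measure harm.

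4. *Timing.* The SAP document history has October 2022 entries made after the primary analysis, which required every participant to have finished or discontinued before the Day 180 visit. An eligibility change at that stage could no longer affect enrolment. This stands as a limit on when the fix is useful.

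**Conclusion.** The point holds. As written, the 160/100 mmHg limit binds only for people on antihypertensive therapy, and untreated people above it are left to investigator judgement under exclusions 4 and 17, with exclusion 5 a weak third. The conclusion rests on the literal wording of the current criterion. The amendment rationale is used only for the purpose of that limit.

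The size in participants is unknown, because the documents do not say how many people screened would be untreated and above the limit. Enrolment of such people is possible, not certain. The consequence is a minor one for patient safety and for consistency between sites. The LDL-C analysis, sample size, power, type I error and estimand are unaffected. The change is still worth making because it costs little and makes a stated safety rule do what its rationale describes.

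**What to change.** In the Protocol summary and in Section 5.2, delete the last three words of criterion 9, or replace them with *with or without antihypertensive therapy*. Keep the 160 and 100 mmHg thresholds.

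The cost is a few words in two places in an amendment made while enrolment is open, and possibly a few additional screen failures. Some of these are recoverable: an excluded person can start antihypertensive treatment, which does not disturb the stability rule for lipid-lowering therapy in inclusion criterion 9, and can use the single re-screening allowed in Section 8.1. Once enrolment has closed, the edit can no longer change who enters the trial.
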